3.3 Provide the scientific or scholarly background for, rationale for, and significance of the research based on the existing literature and how will it add to existing knowledge.

Virtual reality (VR) offers an exciting alternative EF rehabilitation strategy for three reasons. First, VR technology has the capability to offer a multitude of activities for training children with TBI in core EFs⁸ within a versatile virtual environment. Such an enriched, immersive environment has already been shown effective in promoting structural and functional recovery of the human brain.²¹ Furthermore, because all VR-based EF training occurs within a safely controlled, automated virtual environment, it takes minimal physical space and personnel resources to implement in a medical setting, reducing expenses for both the hospitals and the families. Second, VR-based EF training can be readily provided via Internet and mobile platforms. This allows EF training, especially those sessions scheduled after discharge, to be completed without requiring children to leave home. Last but not least, unlike traditional computer-based EF training, we expect VR-based EF training to exert two positive effects on children's rehabilitation²²: (1) improved adherence. VR-based EF training was found especially appealing to pediatric patients in our pilot testing, possibly due to the youth population's increasing exposure to electronic games in recent years; (2) potentially better skill transfer to real life. Although research suggests mixed results of computerized training for cognitive skills in general, we expect VR training to translate trained skills into daily EF skills and overall QoL in pediatric TBI patients because (1) EFs are domain-general cognitive skills that can be gained in one setting and transferred to another;²³ (2) studies using representative national samples of children have supported EF as domain-general skills and documented positive relations between EFs and real-life outcomes,²⁴ and (3) Our pilot test of the VICT program on two pediatric patients with TBI at NCH showed positive changes of core EF scores after intervention (although this preliminary result should be interpreted with caution given that the changes could reflect other factors, such as natural recovery).

The overall goal of the proposed research is to evaluate the feasibility, safety, and efficacy of a VR-based interactive cognitive training (VICT) program in children 7-17 years with complicated mild to

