6.0 Procedures Involved*

The procedure involved for the study is described in detail below:

1) Baseline assessment. All approximately 30 children will complete the NIH Toolbox Cognition Battery tests, CPT 3, Virtual Reality Assessment, and the TBI-QOL Short Form prior to the randomization sequence. Both the assessor and the child will be unaware of group assignment at this point. Additionally, data regarding baseline measurement including proportion of planned baseline measures that are completed and the duration of each assessment will be documented.

2) Intervention. Following the baseline assessment, the approximately 30 children will be randomly assigned to one of the following two groups: intervention group (VICT training) or control group (a comparable VR game without cognitive training). The random allocation sequence will be generated using a SAS-based randomization program with 1:1 allocation ratio and random block sizes of 2 and 4. Both groups will first be provided a tutorial to be familiar with the VR environment. The length of time for either intervention game will be a minimum of 15 minutes of total play. If they are in the hospital, they will play approximately 15 minutes per day during their stay. If they have already been discharged from the hospital, the length of time is a minimum of 15 minutes of total play but can be more spread across their choice of days. Trained researchers who generate the randomization sequence and implement the VR will not participate in any subsequent outcome assessment. Note that although the length of training will vary across children depending on their length of stay or if they have been discharged, this arrangement has unique advantages over a fixed length of training in that: a) it provides consistency with standard therapies children are scheduled to receive, ensuring intervention to meet children's medical needs; and b) it ensures consistent timing and sufficient retention rates for future assessment.

Additionally, AEs and SAEs will be monitored in real-time throughout the intervention. Quantitative user feedback such as sickness, fatigue, and time estimates will be measured at the end of both the first and the last VR session. The

PROTOCOL TITLE: Virtual Reality-based Rehabilitation for Children with Traumatic Brain Injuries

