9.0 Study Timelines*

9.1 Describe:

- **The duration of an individual subject's participation in the study.**
 - An individual subject's participation includes up to three assessment visits (pre-intervention visit, post-intervention visit, and follow-up visit) as well as the intervention training. The assessment visits last approximately 60 minutes per visit. The intervention training will last a minimal of 15 minutes. Since part of the purpose of the study is to explore the dose effect of the intervention, we do not set an upper limit of the intervention length, which could depend on patient's preference and patient's length of stay (if inpatient). We expect the total duration of subject's participation to last up to six months (depending on how far out the subject's follow-up appointment is scheduled upon completion of intervention).
- **The duration anticipated to enroll all study subjects.**
 - Approximately 24 months
- **The estimated date for the investigators to complete this study (complete primary analyses)**
 - August 31, 2021

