17.0 Data Management* and Confidentiality

17.1 Describe the data analysis plan, including any statistical procedures or power analysis.

To examine the research paradigm (Aim 1), we will compute average number of children screened and enrolled per month, proportion of eligible children who enroll, treatment-specific retention rates, proportion of children who adhere to assigned condition, proportion of planned measures that are completed, and average duration of completing each measurement. To examine the feasibility and safety of the VICT program (Aim 2), the total number of AEs/SAEs, mean simulator sickness scores, and mean Borg exertion scores will be computed and compared between the intervention and control group using independent samples t-tests. Additionally, open-end feedback from children, parents, and clinicians on optimizing the VR games and best practices in protocol implementation will be synthesized and submitted to the VR development team for improvement. Finally, to explore the preliminary efficacy of the VICT program (Aim 2), difference scores from baseline to post-intervention and baseline to follow-up of the composite NIH Toolbox score, TBI-QOL, and Conners CPT 3 will be compared between the intervention group and the control group using analysis of covariance (ANCOVA) controlling for baseline scores. BRIEF2, CBCL-APS, and PedsQL (parent/child) scores at follow-up will be compared between the two groups using ANCOVA controlling for baseline scores. Cohen's d for core EFs changes will be computed as the preliminary intervention effect size. Finally, dosage effect will be evaluated within regression analyses, with dosage (0 for controls, cumulative hours of VICT training for intervention group) as the primary predictor and post-intervention NIH Toolbox scores as the outcome variable.

17.2 Describe the steps that will be taken to secure the data (e.g., training, authorization of access, password protection, encryption, physical controls, certificates of confidentiality, and separation of identifiers and data) during storage, use, and transmission.

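### The dose model in section 17.1 codes every control as 0 hours with no arm term, control-game hours or baseline score, so its slope mixes dose with any constant VICT effect and part of any stay-related pattern

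*Combined protocol and SAP*

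**What the plan says.** Section 17.1 says the dosage effect will be examined by regression and defines the terms of the model: "dosage (0 for controls, cumulative hours of VICT training for intervention group) as the primary predictor and post-intervention NIH Toolbox scores as the outcome". It lists no other term for this model. The analyses of covariance in the same paragraph do adjust for baseline scores.

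Controls are not unexposed to VR. Section 6.0, item 2, describes the "control group (a comparable VR game without cognitive training"), and sets a common time rule: "The length of time for either intervention game will be a minimum of 15 minutes of total play". For inpatients, "they will play approximately 15 minutes per day during their stay"; discharged children may spread their play over days they choose.

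Hours are not randomised. Section 6.0 notes that "the length of training will vary across children depending on their length of stay or if they have been discharged". Section 9.1 adds "Since part of the purpose of the study is to explore the dose effect of the intervention, we do not set an upper limit" on intervention length, "which could depend on patient's preference and patient's length of stay (if inpatient").

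Section 27.0 (Confidential Health Information, item 2.0) names age, gender, race, Glasgow Coma Scale, Rancho level, therapy time and neuropsychological results as control variables for the study's analyses in general. Arm, VR hours and length of stay are not listed. Section 17.4 and the recruitment spreadsheet in section 27.0 record dates and times of VR therapy together with study group, and the VR program records game performance automatically.

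**The concern.** Coding controls as 0 is a recognised choice. It gives an unbiased dose slope if the VICT effect starts at zero, rises linearly with hours, and nothing else that affects the score tracks hours. The plan states none of these conditions, and its own design puts the last in doubt, because hours follow length of stay. Section 3.3 itself warns, about the two pilot patients, that "the changes could reflect other factors, such as natural recovery".

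Controls' play time carries at least some of the same stay information, and the coding discards it. With no arm term, a benefit of VICT that does not depend on hours also appears as dose.

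Exploring dose is a stated purpose of the study and the stated reason for setting no upper limit on training (section 9.1). As planned, a reader could not separate three explanations of a slope: more hours help, VICT helps whatever the hours, or children with longer stays changed differently.

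**Working it through.** The plan gives no figure for this model (no SD, effect size, alpha or hours distribution), so there is nothing to reproduce.

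**Step 1: what the slope estimates.** Let A be arm (1 = VICT), H actual VR hours with mean μ and coefficient of variation c, alike in both arms, and D = A × H the planned dosage. Suppose

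Y = a + τA + βAH + γH + error,

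where β is the true dose gradient, τ a constant VICT effect and γ a stay-related pattern per VR hour. With 1:1 allocation (section 6.0):

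- Var(D) = 0.5μ²(1 + c²) − 0.25μ² = 0.5μ²(c² + 0.5)
- Cov(D, A) = 0.25μ
- Cov(D, H) = 0.5c²μ²

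Regressing Y on D alone therefore gives

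slope = β + (τ/μ) × 0.5/(c² + 0.5) + γ × c²/(c² + 0.5).

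The weight on τ/μ is 0.67 at c = 0.5 and 0.33 at c = 1.0. The weight on γ is the complement, 0.33 and 0.67. A simulated sample of 400,000 agreed with the formula.

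**Step 2: assumed base case.** From the documents: about 30 children, 1:1. Assumed: hours = 0.25 + an exponential with mean 1.75 (mean 2, which at 15 minutes per day is 8 inpatient days); baseline-post correlation 0.7; two-sided 5% for illustration. Then c = 1.75/2 = 0.875, c² = 0.766, and the large-sample weights are 0.5/1.266 = 0.40 on τ/μ and 0.766/1.266 = 0.60 on γ. At 30 children the simulated share of γ is lower, about one half.

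**Step 3: simulated trials, 15 per arm (20,000 per scenario).** Slopes are in SD per hour.

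| Scenario | Planned slope | Significant, as written | Significant, plus baseline | Arm × hours significant |
|---|---|---|---|---|
| No effects | 0 | 5% | 5% | 5% |
| τ = 0.3, β = 0 | +0.07 | 8% | 11% | 5% |
| τ = 0.5, β = 0 | +0.12 | 14% | 21% | 5% |
| τ = 0.8, β = 0 | +0.19 | 27% | 43% | 5% |
| γ = +0.15 only | +0.08 | 12% | 17% | 5% |
| γ = −0.15 only | −0.08 | 11% | 17% | 5% |
| β = 0.15 only | 0.15 | 23–24% | 38–39% | 13% |
| β = 0.15, γ = −0.15 | 0.07 | 8% | 10% | 13% |

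With mean hours of 1 or 4, τ = 0.3 gives +0.17 or +0.03. If baseline is omitted and hours correlate with baseline at −0.5 or +0.5, the slope is about −0.11 or +0.11 (14% significant); adding baseline returns the rate to 5%.

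**Step 4: can a real gradient be cancelled?** In the last row the stay pattern removes 0.15 − 0.074 = 0.076, a share of 0.076/0.15 = 0.51. Cancelling β = 0.15 would need γ of about −0.15/0.51 = −0.30 SD/hour, twice the gradient and opposite in sign.

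**Step 5: is an arm term enough?** No. It removes τ, but the slope becomes β + γ. With γ = ±0.15 and no VICT effect it averages ±0.15 and is significant in 23–24% of trials. Control-game hours are needed as well.

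**Step 6: total error at 30 children.** Root-mean-square error, SD/hour:

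| Scenario | Dose + baseline | Arm × hours |
|---|---|---|
| τ = 0.3 | 0.125 | 0.193 |
| τ = 0.5 | 0.164 | 0.194 |
| τ = 0.8 | 0.228 | 0.196 |
| γ = ±0.15 | 0.13 | 0.20 |
| β = 0.15 | 0.097 | 0.195 |
| β = 0.15, γ = −0.15 | 0.130 | 0.195 |

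With no effects, adding baseline alone lowers the planned model's error from 0.138 to 0.100.

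**The case against.** The strongest reply has four parts.

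- **Precision.** At 30 children the interaction model avoids these biases but is so imprecise that dose plus baseline has the smaller total error in most scenarios above; the interaction wins only when the constant effect is large. This stands. A reader might infer that arm × hours should replace the planned model, and the calculations do not support that.
- **Covariates.** Calling dosage the primary predictor leaves room for others, and section 27.0 lists severity and therapy-time variables. If used here, they could absorb some of the stay-related part, so the stay figures are towards the worst case. They could not absorb a constant VICT effect, because arm is not on the list.
- **Control hours.** Hours also follow preference, which may differ between the two games, so control hours need not carry exactly the same information. This stands too. If motivation drives scores in both arms but hours only in the VICT arm (correlation 0.3, 0.5 or 0.7), arm × hours is falsely significant in 8%, 12% or 21% of trials.
- **Stakes.** Section 2.2 states no hypotheses and no endpoint in section 4.0 uses this slope. That limits the weight of the point, but does not remove it, since section 9.1 makes dose a question of the study.

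**Conclusion.** The point holds for the interpretation of the dose slope. The mixing follows from the coding and 1:1 allocation. Its size rests wholly on the assumed hours, SDs, correlation and effects. In the base case, moderate constant effects or stay patterns move the slope by about 0.07 to 0.12 SD/hour, and raise the chance of a significant result with no gradient from 5% to between 8% and 14% as written. The direction of the stay part is unknown, because the documents do not say whether longer stay means more recovery or worse injury.

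Two stronger readings are not supported. One is that the model cancels a real dose effect: that takes a strong opposing pattern, and partial masking or inflation is the likelier result. The other is that the trial's efficacy result is compromised: the randomised analysis of covariance in section 17.1 and the endpoints in section 4.0 do not use this slope. If there is neither a constant effect nor a stay pattern, the planned slope is unbiased and the more precise choice. The change is worth making, for an exploratory analysis.

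**What to change.** In section 17.1:

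1. Add the baseline NIH Toolbox composite to the planned dose model.
2. Keep that model, but label its slope as combining arm and dose effects, not as evidence that more hours help.
3. Beside it, as a sensitivity analysis with a 95% confidence interval, report a model with baseline, arm, actual VR hours in both arms and arm × hours. First confirm that the logged VR dates and times or the automatic game record yield session durations in both arms.
4. Claim a dose effect only if both models point the same way, and state that hours were not randomised.

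It would also help to say which of the section 27.0 control variables, if any, enter the model; one or two at most at this sample size.

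The cost is wording, plus deriving durations from records already planned. The baseline score is already collected. The drawback is precision: the interaction has a standard error of about 0.19–0.20 SD/hour, about 13–14% power at 0.15 SD/hour, and reaches 80% power only at roughly 0.55–0.6 SD/hour. It also stays open to bias from motivation that acts differently by arm. It should be read as an estimate with its interval, next to the planned model.

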18.0 Provisions to Monitor the Data to Ensure the Safety of Subjects*

Not Applicable as the study involves no more than minimal risk to subjects.

19.0 Provisions to Protect the Privacy Interests of Subjects

Password-protected spreadsheet and other electronic databases will be kept in a secure file folder on password protected computers in the Research Institute at Nationwide Children's Hospital. Only researchers on the IRB will have access to the secure folder where the file is located.

Eligible subject information will be entered on a hospital approved password protected computer password protected data registry in a locked research office. Enrolled subjects will be assigned a study ID number which will be how all study documents are labeled. The PI and limited trained research staff will be responsible for maintaining all components of the research record containing participants' identifying information.

We will use several strategies to protect the privacy of participants:

1. Research staff will be trained in the importance of protecting participants' privacy.
2. Each participant will be identified by a unique ID number rather than by name or medical record number. Participants' names will not appear on materials

PROTOCOL TITLE: Virtual Reality-based Rehabilitation for Children with Traumatic Brain Injuries

used during data analysis. The master list of participants' names and corresponding numbers will be kept only in electronic format in a password protected file in a secure folder on password protected computers.

3. All electronic data files will be stored in secure folder on a password-protected computer in a locked research office. Only members of the research team will have access to the files.
4. All hard copies of the data will be kept in a locked file cabinet in a locked office. No hard copies will be kept of the master list of participants' names and corresponding numbers. Only study staff will have access to these documents.
5. Publications of reports will not identify participants in the study or contain information leading to the identification of participants.

We have no plans to contact subjects after their study participation or to share their PHI with other investigators.

20.0 Compensation for Research-Related Injury

Not Applicable as the study involves no more than minimal risk to subjects.

21.0 Economic Burden to Subjects

21.1 Describe any costs that subjects may be responsible for because of participation in the research.

There are no costs that subjects may be responsible for because of participation in the study.

22.0 Consent Process

Researchers from Research Institute at Nationwide Children's Hospital will obtain informed consent from subjects for this research.

Researchers from NCH Center for Injury Research and Policy will work with colleagues throughout various departments/units across the hospital (Inpatient Rehab Unit, Neurosurgery Inpatient Unit, etc.) to identify and approach potential participants admitted to NCH. Other potential participants already discharged will be identified through trauma registry data and mailed invitation letters followed by an introduction phone call. Additional recruitment of discharged patients will be performed at follow up appointments using study flyers. Patients may also self-refer from the public domain through postings on sites such as clinicaltrials.gov (NCT03611062) and through IRB approved recruitment emails. These participants will also be sent the study letter and receive an introduction phone call if they are interested. Once participants have been identified as appropriate for the VR intervention, the research associates will explain and consent the legal guardian and assent the patient if they are 9 or older.

Subjects will only be approached if the subject is interested in learning more about this research. The research associates will ensure that the subjects

PROTOCOL TITLE: Virtual Reality-based Rehabilitation for Children with Traumatic Brain Injuries

understand that participation is voluntary and will not affect any treatment he/she (or their child) may receive in the current or future visits.

When legal guardians are not available to consent, persons who are authorized to consent/sign for medical care as listed on EPIC will provide consent (in addition to the patient's assent if older than 9 years old).

23.0 Process to Document Consent in Writing

Not applicable as this study presents no more than minimal risk of harm to subjects and involves no procedures for which written documentation of consent is normally required outside of the research context.

24.0 Setting

24.1 Describe the sites or locations where your research team will conduct the research.

- *Identify where your research team will identify and recruit potential subjects.*

Subjects will be identified and recruited throughout various departments/units across the hospital (Inpatient Rehab Unit, Neurosurgery Inpatient Unit, etc.). Other potential participants already discharged will be identified through trauma registry data and mailed invitation letters followed by an introduction phone call. Additional recruitment of discharged patients will be performed at follow up appointments using study flyers. Patients may also self-refer from the public domain through postings on sites such as clinicaltrials.gov (NCT03611062) and through IRB approved recruitment emails. These participants will also be sent the study letter and receive an introduction phone call if they are interested.

- *Identify where research procedures will be performed.*

All research procedures will be performed at Nationwide Children's Hospital.

- *Describe the composition and involvement of any community advisory board.*

N/A

25.0 Resources Available

25.1 *Describe the resources available to conduct the research: For example, as appropriate:*

PROTOCOL TITLE: Virtual Reality-based Rehabilitation for Children with Traumatic Brain Injuries

- *Justify the feasibility of recruiting the required number of suitable subjects within the agreed recruitment period. For example, how many potential subjects do you have access to? What percentage of those potential subjects do you need to recruit?*
- *Describe the time that you will devote to conducting and completing the research.*
- *Describe your facilities.*
- *Describe the availability of medical or psychological resources that subjects might need as a result of an anticipated consequences of the human research.*
- *Describe your process to ensure that all persons assisting with the research are adequately informed about the protocol, the research procedures, and their duties and functions.*

